### 5.2.2 Anti-emetics

Patients should be premedicated prior to each treatment cycle of FOLFIRINOX with an HT-3 antagonist and dexamethasone. The addition of aprepitant (Emend) is

strongly encouraged. Other anti-emetics, such as lorazepam may also be provided as clinically necessary.

### 5.2.3 Anti-diarrheals

For symptoms of diarrhea (and/or abdominal cramping), patients will be instructed to take loperamide. This should be started at the earliest sign of loose stool, an increase in bowel movements by 1 to 2 episodes compared to baseline, or an increase in stool volume or liquidity. Dosing is as follows: 4 mg at the first onset of diarrhea, then 2 mg every 2 hours (4 mg every 4 hours at night) until diarrhea-free for at least 12 hours. *Maximum 24-hour dose is 16 mg total.* Additional antidiarrheal measures may be implemented at the discretion of the treating physician. Patients should also be instructed to increase fluid intake to help maintain fluid and electrolyte balance during episodes of diarrhea.

### 5.2.4 Antibiotics

Prophylactic oral antibiotic therapy will not be given at the start of study treatment. However, antibiotics (i.e. oral fluoroquinolones) should be initiated for patients in the following instances: those who have (a) endobiliary stents with an ANC that falls below 500; (b) endobiliary stents who develop a fever above 38.5C; (c) diarrhea persisting for more than 48 hours despite loperamide; (d) fever with diarrhea, regardless of ANC. Administration of long-term prophylactic antibiotics following the first occurrence of any of the above scenarios may be considered only following discussions with the PI or one of the co-PI's.

### 5.2.5 Anticholinergics

Prophylactic use of atropine prior to irinotecan dosing is strongly encouraged and should be on hand for any cholinergic reaction given the higher incidence of this problem in patients receiving irinotecan following oxaliplatin.

## 5.3 Dosing delays/dose modifications

### Dose Modification Guidelines for FOLFIRINOX

These will be based on NCI Common Toxicity Criteria Version 4

\*\* The dose of leucovorin is not modified for toxicity, but may be reduced for shortages.

***Once a dose is decreased, re-escalation is not permitted.*** Patients are off study if they develop the same grade 4 toxicity despite a first dose reduction.

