### 5.3.1b Doses according to subsequent blood counts or in case of infection

ADVERSE EVENTS	REDUCTION OF DOSE FOR SUBSEQUENT CYCLES
Febrile neutropenia or Grade 4 neutropenia (<500) for more than 7 days or Infection with concomitant grade 3-4 neutropenia	1st occurrence: reduce the dose of irinotecan to 150 mg/m   2nd occurrence: reduce also the dose of oxaliplatin to 60 mg/m   3rd occurrence: treatment discontinuation
Grade 3-4 thrombocytopenia [grade 3 <50,000 grade 4 <25,000]	1st occurrence: reduce the oxaliplatin dose to 60 mg/m  and the continuous 5-FU dose to 75 % of the original dose  2nd occurrence: reduce also the dose of irinotecan to 150 mg/m  and the dose of continuous 5FU an additional 25 %  3rd occurrence: treatment discontinuation

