### 5.3.2. Gastrointestinal toxicities

Patients must be instructed in the use of loperamide as treatment for diarrhea, and must have a supply of this drug upon starting mFOLFIRINOX. Patients should not be retreated with irinotecan until recovery from diarrhea (without loperamide for at least 24 h) has occurred.

ADVERSE EVENTS	REDUCTION OF DOSE FOR SUBSEQUENT CYCLES

Diarrhea grade 1-2
 
Diarrhea grade 3-4 or Diarrhea + fever and/or neutropenia grade 3-4
	
No change in doses
 
1st occurrence: reduce the irinotecan dose to 150 mg/m^2
 
2nd occurrence: reduce also the oxaliplatin dose to 60 mg/m^2 and reduce the dose of continuous 5FU to 75 % of the original dose
 
3rd occurrence: treatment discontinuation

Diarrhea ≥ 48 h despite high dose loperamide
	
No reduction of the irinotecan, oxaliplatin or 5FU doses after complete recovery, unless either grade 3-4 diarrhea, or diarrhea + fever, and/or concomitant neutropenia grade 3-4 has occurred

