## 5.4 Duration of Therapy

5.4.1 Including treatment delays due to adverse event(s), as specified in section 5.3, *initial preoperative* chemotherapy treatment with FOLFIRINOX will continue for 4 cycles or until one of the following criteria applies:

- Disease progression,
- Intercurrent illness that prevents further administration of treatment,
- Unacceptable adverse event(s),
- Patient decides to withdraw from the study, or
- General or specific changes in the patient's condition render the patient unacceptable for further treatment in the judgment of the investigator.

5.4.2 Following successful surgery, subsequent FOLFIRINOX will be given for 4 cycles or until one of the aforementioned criteria for stopping applies.

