### 5.6 Criteria for Removal from Study

*Patients will be removed from study when any of the criteria listed in Section 5.4 applies. The reason for study removal and the date the patient was removed must be documented in the Case Report Form.*

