## 8. STUDY CALENDAR

**Schedules shown in the Study Calendar below are provided as an example and should be modified as appropriate.**

Baseline history, physical and blood work are to be conducted within 2 weeks prior to start of protocol therapy. Scans and x-rays must be done  $\leq 4$  weeks prior to the start of therapy. Laboratory evaluations should be repeated within 24 hours prior to initiation of the next cycle of therapy. [ Cycle 1 refers to week of first actual therapy with mFOLFIRINOX.]

	Pre-Study	Cycle 1	Cycle 2	Cycle 3	Cycle 4	Week +4 weeks after Cycle 4 completion	Week +4-6 After Cycle 4 completion	Cycle 5 e	Cycle 6	Cycle 7	Cycle 8	Week +4 after completion of Cycle 8	Off Study d
Informed consent	X												
Demographics	X												
Medical history	X		X	X	X	X		X	X	X	X	X	X
Toxicity Assessment			X	X	X	X			X	X	X	X	
Physical exam	X		X	X	X	X		X	X	X	X	X	X
Vital signs	X	X	X	X	X	X		X	X	X	X	X	X
Height	X												
Weight	X	X	X	X	X	X		X	X	X	X	X	X
Performance status	X	X	X	X	X	X		X	X	X	X	X	X
CBC w/diff, plts	X		X	X	X	X		X	X	X	X	X	X
Serum chemistry a	X		X	X	X	X		X	X	X	X	X	X
Pregnancy test b	X							X					
CA 19-9	X			X		X		X		X		X	X
Radiologic evaluation c	X					X		X				X	
Chemotherapy		X	X	X	X			X	X	X	X		
Surgery							Exact timing per surgeon						

- a. Specific minimal lab tests required –Na, K, Mg, Phosphorus, Glucose, BUN,CO2, Chloride Creatinine, Calcium, Total Protein, Albumin, Total Bilirubin, Alkaline Phosphatase, SGOT, SGPT      b. May be serum or urine.
- c. CT scan of chest/abdomen/pelvis **or** MRI of abdomen/pelvis plus CXR if CT scan cannot be done.
- d. Follow up visits and studies per usual standard of care but not less than every 3 months for years 1-2 and every 6 months for years 3-5.
- e. Cycle 5 starts 4-10 weeks after surgery depending on patient recovery

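### Section 5.3 gives two different instructions for a repeat of the same grade 4 toxicity, and nothing says which one governs

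*Combined protocol and SAP*

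**What the plan says.** The dose-modification guidelines in section 5.3 open with a general rule: "Patients are off study if they develop the same grade 4 toxicity despite a first dose reduction". The closing lines after the neuropathy table in 5.3.7 repeat it and make no exception for the tables.

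Table 5.3.1b has two rows that include grade 4 events. One opens with "Febrile neutropenia or Grade 4 neutropenia" (the latter if it lasts more than 7 days) and adds infection with grade 3-4 neutropenia. Its entry for the 2nd occurrence is "reduce also the dose of oxaliplatin to 60 mg/m"². The other covers grade 3-4 thrombocytopenia; its entry for the 2nd occurrence includes "reduce also the dose of irinotecan to 150 mg/m"² and a further cut in continuous 5-FU. In 5.3.2, the row for grade 3-4 diarrhea has "reduce also the oxaliplatin dose to 60 mg/m"² at the 2nd occurrence, with a 5-FU reduction. All three rows list discontinuation only at the 3rd occurrence.

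Section 5.4 refers to 5.3 only in the words "Including treatment delays due to adverse event(s), as specified in section 5.3" and then lists general stopping criteria, including unacceptable adverse events and investigator judgment. Section 5.6 says "Patients will be removed from study when any of the criteria listed in Section 5.4 applies".

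Section 11.1 counts early withdrawal for toxicity as a failure of the primary endpoint. In section 11.5 only response category 1, preoperative therapy completed with a resection, is a success.

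**The concern.** Both instructions cannot be followed for one patient. If a grade 4 event leads to a first reduction and then recurs at grade 4, the general sentence removes the patient from the study, while the table row keeps the patient on protocol treatment at lower doses.

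Two things are at stake. The first is consistent handling of serious toxicity at the two enrolling institutions. The second is the primary endpoint: the reading chosen can turn a success into a failure in a single-arm trial of at most 21 patients with a binary outcome.

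**Working it through.** **Step 1. The texts side by side.** The case is a patient who has been dose-reduced once for a grade 4 event and then has the same grade 4 event again.

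| Event | General sentence (5.3 opening, end of 5.3.7) | Table row, 2nd occurrence | Table row, 3rd occurrence |
|---|---|---|---|
| Grade 4 neutropenia for more than 7 days (5.3.1b) | Off study | Oxaliplatin also reduced | Discontinue |
| Grade 4 thrombocytopenia, within the grade 3-4 row (5.3.1b) | Off study | Irinotecan also reduced, 5-FU reduced further | Discontinue |
| Grade 4 diarrhea, within the grade 3-4 row (5.3.2) | Off study | Oxaliplatin and 5-FU also reduced | Discontinue |

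The conflict is most direct in the first line, because that trigger is grade 4 by definition. The other two rows pool grades 3 and 4, and neither limits its 2nd step to grade 3. The Day 1 count table in 5.3.1a is triggered by counts rather than by grade 4, so it is not part of this point.

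**Step 2. Search for a precedence statement.** The closing lines of 5.3.7 base dose adjustments on the worst preceding toxicity; this does not rank the off-study sentence against the tables. Section 5.4 cites 5.3 only for delays, and 5.6 points only to 5.4. The reviews and investigator calls in 4.3 and 11.4 are a forum for discussion and set no rule. No precedence statement was found.

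**Step 3. Link to the primary endpoint.** Suppose the repeat comes before cycle 4 is given. Under the general sentence the patient leaves the study early for toxicity, which is a failure under 11.1 and 11.5. Under the table the patient continues, and is a success if cycle 4 and resection follow.

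**Step 4. The design in 11.3.** Inputs: 9 patients at stage 1, stop at 4 or fewer successes; 21 in total, positive at 14 or more; success rates 50% and 75%. The probability of a positive result is

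Σ (x = 5 to 9) P(Bin(9, p) = x) × P(Bin(12, p) ≥ 14 − x).

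This gives 0.8535 at p = 0.75 (plan: at least 0.85) and 0.0893 at p = 0.50, so a negative result has probability 0.9107 (plan: at least 0.90). The plan's figures reproduce.

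**Step 5. Weight of one patient.**
- Stage 1: 1/9 = 11.1 points. Final: 1/21 = 4.8 points (14/21 = 66.7%, 13/21 = 61.9%).
- Exactly 5 of 9: 126 × p⁵ × (1 − p)⁴ = 11.7% at p = 0.75 and 24.6% at p = 0.50.
- Continuing and ending at exactly 14 of 21: Σ (x = 5 to 9) C(9, x) × C(12, 14 − x) = 27,720 + 41,580 + 28,512 + 8,316 + 792 = 106,920. Multiplied by p¹⁴ × (1 − p)⁷, this is 11.6% at p = 0.75 and 5.1% at p = 0.50.

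These are the chances of landing on a boundary where one reclassified patient would change the decision. They are not the chance that such a patient occurs, and the two boundary events overlap, so they should not be added.

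**Step 6. How many patients.** The documents give no rate of repeat grade 4 events. Purely as an assumption, take a rate q per cycle, independent cycles, and no effect of the first reduction. A repeat within cycles 1-3 has probability 3q²(1 − q) + q³ per patient. At q = 2% this is 0.00118, so the chance of at least one such patient among 21 is 1 − (1 − 0.00118)²¹ = 2.5%. The same formula gives 14.2% at q = 5% and 44.9% at q = 10%, but those two rates are hard to square with the protocol's background figures (see the objection).

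**The case against.** The best defence is that the two texts fit together. The off-study sentence is narrow (same toxicity, grade 4, after a reduction) and stands both before and after the tables. Read as an override, it governs same-grade-4 repeats, and the tables govern first events, grade 3 repeats and mixed sequences. Even the neutropenia row keeps some content on this reading: febrile neutropenia followed by infection with grade 3 neutropenia would still reach its 2nd step. This is a possible reading, and it may be what was intended. But it is not written anywhere, and prolonged grade 4 neutropenia has its own explicit 2nd-occurrence instruction. The objection lowers the point from an irreconcilable conflict to an unresolved one; it does not remove it.

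The defence is also right about frequency. Per-cycle rates of 5% and 10% imply that 1 − 0.95⁴ = 18.5% and 1 − 0.90⁴ = 34.4% of patients have at least one event in four cycles. Section 2.1 reports whole-course grade 3/4 rates in metastatic disease of 5.4% for febrile neutropenia and 12.7% for diarrhea. Grade 3/4 neutropenia was higher (45.7%), but the row requires grade 4 for more than 7 days or a complication, and this trial omits the 5-FU bolus and mandates growth factor (5.2.1). The 5% and 10% scenarios should carry no weight.

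**Conclusion.** The inconsistency is real and should be corrected: for a repeat of the same grade 4 toxicity, section 5.3 gives two instructions with different consequences and no order between them. This follows from the text alone and needs no assumed rate. Its numerical effect is unknown and probably small. It matters for the trial's result only if a repeat occurs before cycle 4, the patient would otherwise have completed cycle 4 and been resected, and the count lies at 4 versus 5 of 9 or 13 versus 14 of 21.

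Three stronger readings are tempting but not supported:
- *Off study and treatment discontinuation conflict as terms.* Section 5.6 removes patients from study on the same criteria by which 5.4 ends chemotherapy, so the two are largely tied together. The use of off study in 9.1 for unresectable patients fits that meaning.
- *A repeat after cycle 4 but before surgery cannot be scored.* The calendar places surgery under "Week +4-6 After Cycle 4 completion", so such a case can arise. But a patient who received all four cycles and was resected meets the endpoint as worded and matches category 1 of 11.5.
- *The design loses material power.* A fall in the true success rate from 75% to 70% would lower the probability of a positive result from 0.853 to 0.703. It would require 0.05 × 21 = 1.05 lost successes on average. Nothing in the documents supports a shift of that size, and the two-stage design itself is unaffected.

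**What to change.** The investigators should reconcile the general sentence (opening of 5.3 and end of 5.3.7) with the 5.3.1b rows and the grade 3-4 diarrhea row of 5.3.2, so that one rule of their choosing applies at both sites to a repeat of the same grade 4 toxicity. The text should state which passage takes precedence, and 5.4 and 5.6 should refer to it. Which rule is clinically right is for the investigators, and no view is offered here. The response categories in 11.5 need no change. The cost is amendment wording in 5.3 and cross-references in 5.4 and 5.6; no procedures or patients are added.

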### 5.3.1. Hematologic toxicity

Do not treat until the granulocyte count is  $\geq 1.5 \times 10^9/L$  and the platelet count is  $\geq 75 \times 10^9/L$ .

5.3.1a. Doses according to the blood counts at the beginning of a cycle (Day 1)

Blood counts at D1 of each cycle	DELAY OF CYCLE	DOSE REDUCTION		
		Irinotecan	Oxaliplatin	LV5FU
Granulocytes < 1.5 x 10^9/L	Hold treatment until granulocytes ≥ 1.5 x 10  /L (one or two weeks if necessary).  In case of non recovery after 2 weeks delay, stop treatment*	1st occurrence: reduction of dose to 150 mg/m   2nd occurrence: maintain the dose at 150 mg/m   3rd occurrence: treatment discontinuation	1st occurrence : no reduction of dose  2nd occurrence: reduce the dose to 60 mg/m   3rd occurrence: treatment discontinuation	Any occurrence: no change in 5FU infusion
Platelets < 75 x 10^9/L	Hold the treatment until recovery (platelets ≥75 x 10  /L).  In case of non recovery after 2 weeks delay, stop treatment	1st occurrence : no reduction of dose  2nd occurrence: reduce the dose to 150 mg/m 	1st occurrence: reduce the dose to 60 mg/m   2nd occurrence: maintenance of the reduced dose  3rd occurrence: treatment discontinuation	1st occurrence: reduce the continuous infusion to 75% of the original dose

### 5.3.1b Doses according to subsequent blood counts or in case of infection

ADVERSE EVENTS	REDUCTION OF DOSE FOR SUBSEQUENT CYCLES
Febrile neutropenia or Grade 4 neutropenia (<500) for more than 7 days or Infection with concomitant grade 3-4 neutropenia	1st occurrence: reduce the dose of irinotecan to 150 mg/m   2nd occurrence: reduce also the dose of oxaliplatin to 60 mg/m   3rd occurrence: treatment discontinuation
Grade 3-4 thrombocytopenia [grade 3 <50,000 grade 4 <25,000]	1st occurrence: reduce the oxaliplatin dose to 60 mg/m  and the continuous 5-FU dose to 75 % of the original dose  2nd occurrence: reduce also the dose of irinotecan to 150 mg/m  and the dose of continuous 5FU an additional 25 %  3rd occurrence: treatment discontinuation

### 5.3.2. Gastrointestinal toxicities

Patients must be instructed in the use of loperamide as treatment for diarrhea, and must have a supply of this drug upon starting mFOLFIRINOX. Patients should not be retreated with irinotecan until recovery from diarrhea (without loperamide for at least 24 h) has occurred.

ADVERSE EVENTS	REDUCTION OF DOSE FOR SUBSEQUENT CYCLES

Diarrhea grade 1-2
 
Diarrhea grade 3-4 or Diarrhea + fever and/or neutropenia grade 3-4
	
No change in doses
 
1st occurrence: reduce the irinotecan dose to 150 mg/m^2
 
2nd occurrence: reduce also the oxaliplatin dose to 60 mg/m^2 and reduce the dose of continuous 5FU to 75 % of the original dose
 
3rd occurrence: treatment discontinuation

Diarrhea ≥ 48 h despite high dose loperamide
	
No reduction of the irinotecan, oxaliplatin or 5FU doses after complete recovery, unless either grade 3-4 diarrhea, or diarrhea + fever, and/or concomitant neutropenia grade 3-4 has occurred

### 5.3.3 Mucositis or “hand-foot” syndrome

In case of grade 3-4 toxicity, a reduction in dosage of 25% of continuous 5FU will be carried out for the subsequent cycles.

### 5.3.4 Cardiac toxicity

*In case of angina pectoris or of myocardial infarction, 5FU and leucovorin has to be stopped.*

### 5.3.5 Increase in bilirubin

In case of elevation of bilirubin, it is essential to exclude an obstruction of the biliary stent or progressive disease and to postpone chemotherapy. If bilirubin is  $\geq 1.5 \times \text{ULN}$ , irinotecan is held and should not be given until bilirubin is  $\leq 1.5 \times \text{ULN}$ .

### 5.3.6 Other toxicities

Any other toxicity  $\geq$  grade 2, except anemia and alopecia, may require a reduction in the dose of irinotecan to 150 mg/m^2 and/or oxaliplatin to 60mg/m^2 and/or 5FU of 25% depending on the type of adverse event.

### 5.3.7 Peripheral neuropathy

*The dose of oxaliplatin should be adjusted according to the table below:*

Toxicity	Duration of the toxicity		
	$\leq 7$ days	$>7$ days and $<14$ days	Persistent between the cycles
Paraesthesia/dysesthesia without functional impairment (grade 1 NCI)	No change	No change	No change
Paraesthesia/dysesthesia with functional impairment but not impeding the activities of the daily lives (grade 2 NCI)	No change	No change	65 mg/m 
Paraesthesia/dysesthesia with pain or functional impairment impeding the activities of daily life (grade 3 NCI)	65 mg/m 	65 mg/m 	Stop oxaliplatin
Paraesthesia/dysesthesia persistent, disabling	Not applicable	Not applicable	Stop oxaliplatin

If the oxaliplatin is stopped for neurotoxicity, irinotecan and the 5-FU will be continued.

**Once the dose of any drug has been decreased, re-escalation is not permitted.**

Patients are off study if they develop the same grade 4 toxicity despite a first dose reduction.

All dose adjustments should be based on the worst preceding toxicity, graded using the National Cancer Institute Common Toxicity Criteria (version 4.0).

## 5.4 Duration of Therapy

5.4.1 Including treatment delays due to adverse event(s), as specified in section 5.3, *initial preoperative* chemotherapy treatment with FOLFIRINOX will continue for 4 cycles or until one of the following criteria applies:

- Disease progression,
- Intercurrent illness that prevents further administration of treatment,
- Unacceptable adverse event(s),
- Patient decides to withdraw from the study, or
- General or specific changes in the patient's condition render the patient unacceptable for further treatment in the judgment of the investigator.

5.4.2 Following successful surgery, subsequent FOLFIRINOX will be given for 4 cycles or until one of the aforementioned criteria for stopping applies.

### 5.5 Duration of Follow Up

Patients will be followed every 3 months for 2 years and every 6 months for years 3-5 after completion or removal from study or until death, whichever occurs first.

Patients removed from study for unacceptable adverse event(s) will be followed until resolution or stabilization of the adverse event.

### 5.6 Criteria for Removal from Study

*Patients will be removed from study when any of the criteria listed in Section 5.4 applies. The reason for study removal and the date the patient was removed must be documented in the Case Report Form.*

## 6. ADVERSE EVENTS: LISTING AND REPORTING REQUIREMENTS

Adverse event (AE) monitoring and reporting is a routine part of every clinical trial. The following list of AEs (Section 6.1) and the characteristics of an observed AE (Section 6.2) will determine whether the event requires expedited reporting to the local IRB (NorthShore or University of Chicago), to the data manager at NorthShore ([name]) and to MedWatch **in addition** to routine reporting.

### 6.1. Adverse Event Lists for Commercial Agents

#### 6.1.1 Common, expected adverse events

5FU/leucovorin: diarrhea, esophagopharyngitis, leukopenia, infection, ulcerative stomatitis, gastrointestinal ulceration, thrombocytopenia, acute cerebellar

syndrome, myocardial ischemia, palmar-plantar erythrodysesthesia, and pneumopathy

Oxaliplatin: anemia, arthralgia, chest pain, dehydration, dyspnea, edema, hand-foot syndrome, hypokalemia, injection site reaction, leukopenia, neutropenia, neuropathy, cold sensitivity, persistent cough, pulmonary fibrosis, stomatitis, thrombocytopenia, thromboembolism.

Irinotecan: anemia, diarrhea with or without abdominal cramping and sweating, dyspnea, fever, abdominal enlargement, dehydration, edema, upper respiratory tract infection, neutropenic fever, stomatitis, allergic reactions, including anaphylactoid reactions, and thrombocytopenia

### 6.1.2 Comprehensive list of adverse events

Please refer to the professional package inserts for a comprehensive list of adverse events.

## 6.2 Adverse Event Characteristics

- **CTCAE term (AE description) and grade:** The descriptions and grading scales found in the revised NCI Common Terminology Criteria for Adverse Events (CTCAE) version 4.0 will be utilized for AE reporting. All appropriate treatment areas should have access to a copy of the CTCAE version 4.0. A copy of the CTCAE version 4.0 can be downloaded from the CTEP web site <http://ctep.cancer.gov/>
- **‘Expectedness’:** AEs can be ‘Unexpected’ or ‘Expected’ (see Section 6.1 above) for expedited reporting purposes only.
- **Attribution** of the AE:
  - Definite – The AE *is clearly related* to the study treatment.
  - Probable – The AE *is likely related* to the study treatment.
  - Possible – The AE *may be related* to the study treatment.
  - Unlikely – The AE *is doubtfully related* to the study treatment.
  - Unrelated – The AE *is clearly NOT related* to the study treatment.

